[Part 1 of 4 of the document. The other parts are not shown.]

Official Title: A Phase 3, Open-Label, Single-Arm Study To Evaluate The Efficacy And Safety Of

BMN 270, An Adenovirus-Associated Virus Vector-Mediated Gene Transfer Of Human Factor VIII In Hemophilia A Patients With Residual FVIII Levels ≤ 1

IU/dL Receiving Prophylactic FVIII Infusions

NCT Number: NCT03370913

Applicant/MAH: BioMarin Pharmaceutical Inc.

Version Date: 15 Jul 2021

Note to File (NTF)

Project No.:	BMN 270; Study 270-301
Project Name (If Applicable):	To align the 270-301 Protocol (version 7.0, 15 July 2021; US-specific) and the 2-year analysis SAP (version 2.0, 13 December 2021) with the 2-year 270-301 CSR
Location:	NA
Subject:	NTF to bridge the 270-301 protocol (version 7.0, 15 July 2021; US-specific) and the 2-year analysis SAP (version 2.0, 13 December 2021) with the 2-year 270-301 CSR for primary and secondary endpoints and other changes made to the 2-year analyses.
Date	02 March 2023

Overserved Discrepancy – Primary and secondary endpoints and statistical analysis methods used in the 2-year 270-301 CSR were modified from those specified in the effective versions of the 270-301 protocol (version 7.0, 15 July 2021; US-specific) and the 2-year analysis SAP (version 2.0, 13 December 2021).

Background – The 2-year analysis of Study 270-301 was performed in January 2022 based on pre-specified analysis methods in the 2-year analysis SAP. Type B Pre-BLA feedback was received from FDA on 16 May 2022. FDA requested changes to the analysis methods, including primary and secondary endpoints. The results reported in 2-year 270-301 CSR reflect the modified analysis methods per FDA feedback and this CSR was submitted to the FDA on 29 September 2022, in the BLA re-submission. Changes from the planned analysis methods were documented in Section 9.8.2 of the CSR (Changes to Planned Analyses).

Solution – This NTF serves as a bridging document between the analysis methods in the 270-301 protocol (version 7.0, 15 July 2021; US-specific), the 2-year analysis SAP (version 2.0, 13 December 2021) and the 2-year 270-301 CSR.

The table below outlines all the changes made to the 2-year analysis methods, including primary and secondary endpoints

	Changes to planned 2-yr A	nalyses for 270-301 based on I	FDA feedback
	270-301 Protocol (version 7.0, 15 July 2021; US- specific)	2-year Analysis SAP (version 2.0, 13 December 2021)	270-301 2-Year CSR (in response to FDA Feedback)
Primary and secondary efficacy endpoints	Primary ABR (treated bleeds) Secondary FVIII activity FVIII utilization (If discrepancies exist in statistical methods between the SAP and the study protocol, the SAP will prevail)	Primary ABR (treated bleeds) Secondary FVIII activity FVIII utilization ABR (all bleeds) Haemo-QoL-A Total score Haemo-QoL-A Physical Functioning domain score Haemo-QoL-A	Primary

		Consequences of bleeding domain score • Haemo-QoL-A Role functioning domain score	Haemo-QoL-A Role functioning domain score
Hypothesis testing	Hierarchical testing will be performed in the order of endpoints as shown above, each at the alpha level of 0.0498. (If discrepancies exist in statistical methods between the SAP and the study protocol, the SAP will prevail)	Hierarchical testing will be performed in the order of endpoints as shown above, each at the alpha level of 0.05.	At the time of receipt of FDA WRO feedback, the outcomes of the SAP-specified hypothesis testing were known to the Sponsor - all statistically significant at the alpha level of 0.05. By considering ABR (all bleeds) as the primary efficacy endpoint, the revised analyses will simply present the study results with pvalues to show statistical significance on each endpoint.
Ranking of secondary efficacy endpoints	Secondary efficacy endpoints are ranked in hypothesis testing order as shown above. (If discrepancies exist in statistical methods between the SAP and the study protocol, the SAP will prevail)	Secondary efficacy endpoints are ranked in hypothesis testing order as shown above.	Secondary efficacy endpoints are not ranked, and their results will be presented one by one.
Sensitivity analysis: impact of exogenous FVIII product use in the efficacy evaluation period (EEP) on ABR		Not planned	The following sensitivity analyses will be performed by counting exogenous FVIII product use in EEP as bleeding events: • #1: count each one- time FVIII prophylaxi use in EEP as one bleed • #2: count each one- time or routine FVIII prophylaxis use in EEP as one bleed #3: count each one-time or routine FVIII prophylaxis use and each surgery/procedure that had FVIII use in EEP as one bleed
Additional sensitivity analysis: impact of IS on ABR and FVIII activity		Not planned	The following sensitivity analyses will be performed in subjects who have been off IS for at least 12 months Repeat the primary analysis of ABR (ABI

			change from baseline) in this subgroup Repeat the primary analysis of FVIII activity (FVIII activity change from baseline at Week 104) in this subgroup
Washout period between the last dose of FVIII prophylaxis following gene therapy and the start of EEP	No washout period	3 days	Based on the half-life of the original FVIII prophylaxis product: • 3 days for standard half-life or plasmaderived products • 5 days for extended half-life
Definition of AEs/SAEs related to IS		All AEs/SAEs during or within 2 weeks' post-IS use	All AEs/SAEs following IS use up to each subject's last visit for the analysis
IS (CS or AIS) therapy to be included in the analysis		Systemic IS (CS or AIS) indicated for ALT elevation of any duration, or indicated for other purposes with a duration of at least 4 weeks	Systemic IS (CS or AIS) indicated for any purpose of any duration
Definition of an IS course (cycle)		The start of an IS use through the end of taper or increase in IS dose for ≥ 2 consecutive weeks preceded by at least 2 decreases in IS dose, whichever occurs earlier	The time period between the first day of starting an IS therapy to the last day of IS use. Any increase in the dose of IS will be considered as a new cycle of IS therapy with the first day of increase of IS dose constituting as the start day of a new cycle.

Comment(s)/ Recommendation(s):

This NTF serves as a bridging document between the analysis methods in the 270-301 protocol (version 7.0, 15 July 2021; US-specific), the 2-year analysis SAP (version 2.0, 13 December 2021) and the 2-year 270-301 CSR.

16-Mar-2023 | 5:35 PM PDT

PI , MD, PhD
PI , Clinical Sciences
BioMarin Pharmaceutical Inc.

PI , Regulatory Affairs BioMarin Pharmaceutical Inc.

CLINICAL STUDY PROTOCOL

Study Title: A Phase 3 Open-Label, Single-Arm Study To Evaluate The Efficacy

and Safety of BMN 270, an Adeno-Associated Virus Vector— Mediated Gene Transfer of Human Factor VIII in Hemophilia A Patients with Residual FVIII Levels ≤ 1 IU/dL Receiving

Prophylactic FVIII Infusions

Protocol Number: 270-301

Active Investigational Product: AAV5-hFVIII-SQ

IND/European Union Drug Regulating Authorities Clinical Trials (EudraCT) Number: 2017-003215-19 IND #: 017659

Indication: Hemophilia A

Sponsor: BioMarin Pharmaceutical Inc.

[name]

Development Phase: Phase 3

Sponsor's Responsible Medical

Monitor:

MD, MPhil

BioMarin Pharmaceutical Inc.

[name]

Duration of Subject

Participation:

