7.4 Summary of Overall Risks and Benefits

The majority of subjects in the ongoing 270-201 clinical study who have received 4E13 or 6E13 vg/kg doses of BMN 270 have had Grade 1 asymptomatic elevations in ALT. For most subjects, the elevations have reached only slightly above the ULN. Based on the effectiveness of transient oral corticosteroid use to suppress a presumed Class 1 (cytotoxic T-cell) response to hepatocytes transduced in prior studies with hepatic transduction with AAV vectors (Mingozzi, 2013), subjects were treated with 7-32 weeks of oral corticosteroids preventatively or in response to the elevations in ALT to ensure preservation of the transduced hepatocytes. Using this approach, no sustained loss of FVIII activity has been observed in subjects with ALT elevations, consistent with maintaining a high level of hepatocyte function. Moreover, the rise in ALT levels were not accompanied by significant or lasting aberrations in other liver function tests such as AST, bilirubin or albumin, indicating that extent of toxicity is limited. Overall, the literature suggests that transient elevations in liver enzymes are expected following AAV-based gene therapy for the treatment for hemophilia B without any long-term concerns of hepatic injury (Manno, 2006, Nature Med); (Nathwani, 2011, N Engl J Med); (George, 2016, Haemophilia); (Miesbach, 2016, Haemophilia).

At the highest dose tested in 270-201 (6E13 vg/kg), the majority of subjects achieved FVIII levels above 50 IU/dL at 52 weeks post-infusion. Subjects in that cohort also reported markedly decreased bleeding compared with pre-study rates and the ability to discontinue prophylactic FVIII infusions. Subjects at all dose levels continue to be followed.

The current data available for BMN 270 does not yet permit adequate assessment of the benefit:risk profile of this investigational drug. Given the monitoring measures in place in the clinical protocol(s) to minimize the risk to subjects participating in the existing studies, the identified risks are justified by the anticipated benefits that may be afforded to subjects. Each subject in 270-301 will have a comprehensive surveillance plan that monitors LFTs during the study, and elevations in LFT will be addressed according to the guidelines set forth in the protocol. Safety will be assessed by adverse event reporting and clinical laboratory assessments.

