- ^e Blood samples will be collected from subjects to evaluate biochemical, molecular, cellular, and genetic/genomic aspects relevant to hemophilia A disease. The exploratory genetic/genomic testing on these samples is optional.

^a Complete physical examination should be performed at Week 52 and every 52 weeks thereafter; brief physical exam may be performed at other study visits. Weight should be recorded at Week 36 and every 4 weeks through Week 52, then every 6 months during Years 2-5.

BIOMARIN 270-301 Page 43	
--------------------------	--

^f PRO assessments during Years 2-5 of Long-Term Follow-up should be performed at every other visit (every 6 months) starting with the Week 78 visit (ie, 26 weeks after the Week 52 visit at the end of Year 1 of the Long-Term Follow-up period).

BIOMARIN	270-301	Page 44
----------	---------	---------

Table 9.1.5: Schedule of Events – Therapeutic Corticosteroids for LFT Elevations or Decreased FVIII Activity

[figure not shown]
	Steroid Treatment Period ^b								Post-Steroid Period ^c				
	Week 1	Week 2	Week 3	Week 4	Week 5	Week 6	Week 7	Week 8 ^b	Week 1	Week 2	Week 3	Week 4	Week 13
Therapeutic corticosteroids (dose in mg/day) a	60 mg	60 mg	40 mg	40 mg	40 mg	30 mg	20 mg	10 mg					
FVIII activity testing									X	X	X	X	
Liver function testing									X	X	X	X	
Hepatitis B testing ^d						X			X				X
HCV Viral Load ^d						X			X				X

^a Therapeutic oral corticosteroids may be initiated according to the parameters set out in Section 9.4.8.2.

^b Following initiation or completion of steroid regimen, if a recurrence of ALT values > 1.5x ULN is reported, steroid management decisions will based on discussions between the Investigator and Medical Monitor. Modification of the steroid regimen may take into consideration possible confounders for the ALT elevation, relationship between increases in ALT and FVIII activity, ALT/FVIII levels post steroid initiation, and adverse events related to steroid dosing. Guidance for tapering oral corticosteroid dosing can be found in Section 9.4.8.2.

^c After discontinuation of oral corticosteroids, weekly labs for ALT and FVIII levels will be measured once a week for 4 weeks to ensure stability in values. If these assessments are already being done as part of normal study follow-up, they do not need to be duplicated.

^d Should only be performed in subjects with a history of hepatitis B or hepatitis C.

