10.1.1 Adverse Events

For this protocol, an adverse event (AE) is any untoward medical occurrence in a subject, temporally associated with the use of study intervention, whether or not considered related to the study intervention.

[figure not shown]
An AE can therefore be any unfavorable and unintended sign (including an abnormal laboratory finding), symptom, or disease (new or exacerbated) temporally associated with the use of study intervention.

Events meeting the AE definition include:

- Exacerbation of a chronic or intermittent pre-existing condition including either an increase in frequency and/or intensity of the condition.
- New conditions detected or diagnosed after study intervention administration even though it may have been present before the start of the study.
- Signs, symptoms, or the clinical sequelae of a suspected drug-drug interaction.

Events not meeting the AE definition include:

- Any clinically significant abnormal laboratory findings or other abnormal safety assessments which are associated with the underlying disease, unless judged by the investigator to be more severe than expected for the participant's condition.
- The disease/disorder being studied or expected progression, signs, or symptoms of the disease/disorder being studied, unless more severe than expected for the participant's condition.
- Medical or surgical procedure (eg, endoscopy, appendectomy): the condition that leads to the procedure is the AE.
- Situations in which an untoward medical occurrence did not occur (social and/or convenience admission to a hospital).
- Anticipated day-to-day fluctuations of pre-existing disease(s) or condition(s) present or detected at the start of the study that do not worsen.

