Table 9.1.5: Schedule of Events – Therapeutic Corticosteroids for LFT Elevations or Decreased FVIII Activity

			St	eroid Treat	tment Perio	od ^b				Post	-Steroid Pe	riod ^c	
	Week 1	Week 2	Week 3	Week 4	Week 5	Week 6	Week 7	Week 8 ^b	Week 1	Week 2	Week 3	Week 4	Week 13
Therapeutic corticosteroids (dose in mg/day) ^a	60 mg	60 mg	40 mg	40 mg	40 mg	30 mg	20 mg	10 mg					
FVIII activity testing									X	X	X	X	
Liver function testing									X	X	X	X	
Hepatitis B testing ^d						X			X				X
HCV Viral Load ^d						X			X				X

^a Therapeutic oral corticosteroids may be initiated according to the parameters set out in Section 9.4.8.2.

^b Following initiation or completion of steroid regimen, if a recurrence of ALT values > 1.5x ULN is reported, steroid management decisions will based on discussions between the Investigator and Medical Monitor. Modification of the steroid regimen may take into consideration possible confounders for the ALT elevation, relationship between increases in ALT and FVIII activity, ALT/FVIII levels post steroid initiation, and adverse events related to steroid dosing. Guidance for tapering oral corticosteroid dosing can be found in Section 9.4.8.2.

^c After discontinuation of oral corticosteroids, weekly labs for ALT and FVIII levels will be measured once a week for 4 weeks to ensure stability in values. If these assessments are already being done as part of normal study follow-up, they do not need to be duplicated.

^d Should only be performed in subjects with a history of hepatitis B or hepatitis C.

Page 50

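### The Note to File labels AEs and SAEs as related to immunosuppressant (IS) use on time order alone, with no end to the window, so background events count as IS-related by construction

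*Protocol*

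**What the plan says.** The Note to File carries a table of changes to the planned 2-year analyses. Its row defining AEs and SAEs related to IS gives the rule planned in SAP v2.0, "All AEs/SAEs during or within 2 weeks' post-IS use", and the rule used in the 2-year CSR, "All AEs/SAEs following IS use up to each subject's last visit for the analysis". The next row widens which IS counts. SAP v2.0 took IS for ALT elevation of any duration, or IS for other purposes lasting at least 4 weeks; the CSR takes "Systemic IS (CS or AIS) indicated for any purpose of any duration". The Note attributes these changes to FDA feedback received in May 2022.

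Section 10.1.1 of the protocol makes the event side equally broad: "an adverse event (AE) is any untoward medical occurrence in a subject, temporally associated with the use of study intervention, whether or not considered related". Section 9.4.8.2 uses relatedness to corticosteroids differently, for events that are suspected of being caused by them. The causality guidance in Section 10.3.3.3 concerns the investigational product, and it classes an event with no reasonable time relation as not related.

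**The concern.** The row heading claims relatedness, but the rule has one input: whether the event came after IS use. It does not ask whether the subject was still on IS, how long ago IS stopped, or whether anyone suspected IS. For subjects given IS, the IS-related count is therefore the all-cause count after IS use.

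The Note itself treats long time off IS as a separate state when it looks at efficacy: it adds a sensitivity analysis in subjects off IS for at least 12 months. Under the safety rule, an AE in that same period is still labelled as related to IS.

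Safety conclusions in this trial rest on descriptive tables, so what a table is called matters. A reader of this one could overstate the burden of IS, and real on-treatment effects would be mixed with unrelated later events.

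**Working it through.** The documents give no figure for this rule, so there is none to reproduce. The check asks what the rule counts when IS has no effect at all.

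Inputs from the documents:
- End of window: Week 104, the time point in the Note's IS sensitivity analysis ("FVIII activity change from baseline at Week 104"). Subjects with a later last visit would have a longer window.
- Short course: 8 weeks, from Table 9.1.5 ("Schedule of Events – Therapeutic Corticosteroids for LFT Elevations or Decreased FVIII Activity"), the same length in the original protocol and Amendment 1.
- Long course: 32 weeks, the upper end reported from Study 270-201 in Section 7.4 ("subjects were treated with 7-32 weeks of oral corticosteroids preventatively or in response to the elevations in ALT").
- SAP v2.0 window: course plus 2 weeks, so 10 or 34 weeks.

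Assumptions not in the documents: the window opens at the first IS dose; IS starts at Week 8 or Week 26; AEs occur at a constant background rate of 0.5, 1 or 2 per subject-year, and SAEs at 0.05, 0.1 or 0.2.

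**Step 1, window length T.** 104 - 8 = 96 weeks; 104 - 26 = 78 weeks.

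**Step 2, ratio of expected background events, CSR window to SAP window.** At a constant rate, the rate cancels.
- 8-week course: 96/10 = 9.6 and 78/10 = 7.8.
- 32-week course: 96/34 = 2.8 and 78/34 = 2.3.
- For the 8-week course, the share of counted time outside the SAP window is (96 - 10)/96 = 90% and (78 - 10)/78 = 87%.

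**Step 3, share of IS-treated subjects with at least one labelled AE.** With Poisson events, P = 1 - exp(-rate x T/52). For strong differences between subjects (gamma-Poisson, shape 1), P = 1 - 1/(1 + rate x T/52). For example, at 2 per year and T = 78, Poisson gives 1 - exp(-3) = 95.0%.

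| AEs per year | CSR window, Poisson (start Week 26 to Week 8) | CSR window, strong heterogeneity | SAP window, 8-week course, Poisson | SAP window, 32-week course, Poisson |
|---|---|---|---|---|
| 0.5 | 52.8-60.3% | 42.9-48.0% | 9.2% | 27.9% |
| 1 | 77.7-84.2% | 60.0-64.9% | 17.5% | 48.0% |
| 2 | 95.0-97.5% | 75.0-78.7% | 31.9% | 73.0% |

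**Step 4, background rate at which 95% of IS-treated subjects are counted.** Poisson: -ln(0.05) x 52/T = 1.6 per year (start Week 8) or 2.0 (start Week 26). With strong heterogeneity: 19 x 52/T = 10.3 or 12.7 per year.

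**Step 5, SAEs.** With start at Week 8, the Poisson share is 8.8%, 16.9% and 30.9% at 0.05, 0.1 and 0.2 per year.

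**The case against.** A reader might infer that nearly every IS-treated subject will carry an IS-related event whatever IS does. The documents do not support that. They give no background AE rate, no IS start dates and no share of subjects on IS. Steps 3 to 5 show that the share can be near one half, needs about 1.6 to 2 AEs per year with little heterogeneity to reach 95%, and is far lower for SAEs. A reader might also treat the rule as a test with a false-positive rate. It is not one: the safety analysis is primarily descriptive, and the row sets no threshold or decision.

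Other points have weight:
- The 8-week course comes from protocol versions earlier than v7.0, which the Note bridges. IS practice had widened by then, since the Note counts agents other than corticosteroids. The 7.8 to 9.6 multiple is therefore illustrative for the 2-year analysis.
- The wording does not say whether the window opens at the first or the last IS dose. Every figure above assumes the first. On the other reading, events during IS would drop out.
- The change is presented as regulator-driven, and a longer window can catch late-onset effects. That is a sound reason to keep the tabulation.
- The Note says the 2-year analysis was run in January 2022 by the SAP methods, so the narrower tabulation may exist. Section 9.4.8.2 also has steroid-suspected events reported. The SAP and CSR are not at hand, so neither can be confirmed as shown beside this definition.
- The SAP v2.0 window is itself temporal. It bounds the lag from exposure; it does not establish cause.

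These points limit the size and the remedy. They do not make the label accurate.

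**Conclusion.** The point holds as a labelling and interpretation defect. The row claims relatedness, but the rule tests only time order, has no end after IS stops, and is opened by any systemic IS of any duration. Background events are counted as IS-related by construction at any background rate above zero.

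How much this inflates the count is conditional. The multiples of 7.8-9.6 (8-week course) and 2.3-2.8 (32-week course) do not depend on the background rate, provided it is constant. They do rest on the assumed IS start, the Week 104 end, the course length and a window opening at the first dose. The subject-level shares rest in addition on the assumed AE rates and on how evenly events are spread across subjects.

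**What to change.** Keep the regulator-requested tabulation, but:
- title it *AEs/SAEs after first IS use*, and state that the window opens at the first IS dose;
- report the SAP v2.0 window (on IS or within 2 weeks after) beside it;
- add AE and SAE rates per person-year for three periods: on IS or within 2 weeks after, later than 2 weeks after IS, and before or never on IS.

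The cost is a changed title and one or two more tables. The Note already defines the first and last day of an IS course, and the narrower window was already specified, so no new data are needed. Two cautions belong in the footnotes. Late-onset IS effects may fall in the later period. The three rates are descriptive, because AE visits thin from weekly in the early months to every 4 weeks in Year 2 and IS is often started in response to ALT elevation, so the periods differ in more than IS exposure.

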2 SYNOPSIS

NAME OF COMPANY	SUMMARY TABLE	FOR NATIONAL
BioMarin Pharmaceutical Inc.	Referring to Part of the	AUTHORITY USE
[name]	Dossier:	ONLY:
[name]		
	Volume:	
NAME OF FINISHED PRODUCT:		
BMN 270	Page:	
NAME OF ACTIVE INGREDIENT:	Reference:	
AAV5-hFVIII-SQ		

TITLE OF STUDY:

A Phase 3 Open-Label, Single-Arm Study To Evaluate The Efficacy and Safety of BMN 270, an Adeno-Associated Virus Vector–Mediated Gene Transfer of Human Factor VIII in Hemophilia A Patients with Residual FVIII Levels ≤ 1 IU/dL Receiving Prophylactic FVIII Infusions

PROTOCOL NUMBER:

270-301

STUDY SITES:

Approximately 30 sites worldwide.

PHASE OF DEVELOPMENT:

Phase 3

STUDY RATIONALE:

Hemophilia A (HA) is an X-linked recessive bleeding disorder that affects approximately 1 in 5,000 males. It is caused by deficiency in the activity of coagulation factor VIII (FVIII), an essential cofactor in the intrinsic coagulation pathway. This disorder can be either inherited, due to a genetic aberrancy, or an acquired immunologic process, leading to insufficient quantities of FVIII or a dysfunctional FVIII, but all are characterized by a defective coagulation process. The clinical phenotype of HA patients generally correlates tightly with the level of residual expression. Severe HA is classified as FVIII activity less than 1% of wild-type (< 1 IU/dL), moderate disease comprises 1-5% of wild-type activity and the mild form is 5-40% activity. The clinical manifestations of severe HA are frequent spontaneous bleeding episodes, predominantly in joints and soft tissues, with a substantially increased risk of death from hemorrhage when the brain is involved. Subjects with moderate disease can exhibit manifestations similar to those seen in patients with severe HA, resulting in a comparable bleeding phenotype.

Treatment of severe HA presently consists of intravenous injection of plasma-derived or recombinant human FVIII protein (rhFVIII) concentrates, both as prophylaxis 2-3 times per week, and at the time of a bleed, to prevent or control bleeding episodes, respectively. The half-life for FVIII (12 to 18 hours for most approved products) necessitates frequent infusions, and although a major advance in the treatment of HA, it remains common for severe HA patients to continue to have multiple bleeding events on prophylactic therapy (median ABR of 1-4 with prophylaxis treatment in a recently published retrospective observational study (Berntorp, 2016, Haemophilia) and between 1-2 in 6 prospective FVIII interventional studies) and on-demand-only therapy (median ABR of 4.5-18 in a recently published retrospective study (Berntorp, 2016,

BIOMARIN	270-301	Page 3
----------	---------	--------

NAME OF COMPANY **SUMMARY TABLE** FOR NATIONAL BioMarin Pharmaceutical Inc. Referring to Part of the **AUTHORITY USE** [name] Dossier: **ONLY:** [name] Volume: NAME OF FINISHED PRODUCT: **BMN 270** Page: NAME OF ACTIVE INGREDIENT: Reference: AAV5-hFVIII-SQ

[figure not shown]
Haemophilia) and between 20-60 in 6 prospective FVIII interventional studies). The consequence of multiple bleeding events is the development of debilitating multiple-joint arthropathy and substantially increased risk of death. Chemical modification (eg, direct conjugation of polyethylene glycol (PEG) polymers) and bioengineering of FVIII (eg, FVIII-Fc fusion proteins) improve half-life by approximately 50%, and thus, show promise in reduced dosing and maintaining activity levels above a 1% trough for a greater proportion of the dosing interval. However, patients with severe HA who are treated with extended half-life FVIII remain dependent on multiple infusions to maintain critical levels of FVIII activity. There is therefore a strong unmet need for a fully preventive treatment of HA to give patients a FVIII level compatible with a normal and hemorrhage-free life.

Gene therapy offers the potential of disease-modifying therapy by continuous endogenous production of active FVIII following a single intravenous infusion of a vector encoding the appropriate gene sequence for long-term episomal expression. Hemophilia A is well-suited for a gene replacement approach because clinical manifestations are attributable to the lack of a single gene product (FVIII) that circulates in minute amounts (200 ng/ml) in the plasma. Tightly regulated control of gene expression is not essential, and even modest increases in the level of FVIII (any increase of the plasma level by 2 ng/ml induces an increase in activity of 1%) can ameliorate the severe form of hemophilia A. Thus, relatively small changes in endogenous FVIII activity can result in clinically relevant improvements in disease phenotype. Finally, the circulating FVIII response to gene transduction can be assessed using validated quantitative rather than qualitative endpoints that are easily assayed using established laboratory techniques. Several different gene transfer strategies for FVIII replacement have been evaluated, but adeno-associated viral (AAV) vectors show the greatest promise. They have an excellent and well-defined safety profile, and can direct long-term transgene expression with tropism and promoter specificity for specific tissues, such as the liver (for serotypes 2, 5 and 8 among others). Indeed, an ongoing gene therapy clinical trial for a related disorder, hemophilia B, has established that stable (median follow-up of 3.2 years) expression of human factor IX (hFIX) at levels that are sufficient for conversion of their bleeding phenotype from severe to moderate or mild is achievable following a single peripheral vein infusion of AAV8-hFIX vector. Several participants in this trial have been able to discontinue factor prophylaxis without suffering spontaneous hemorrhages, even when they undertook activities that previously resulted in bleeding. Thus, gene therapy treatment has resulted in a substantial improvement in their quality of life (Nathwani, 2014, N Engl J Med). BMN 270 is an AAV5-based gene therapy vector that expresses the SQ form of hFVIII under the control of a hybrid human liver-specific promoter (Figure 1).

BIOMARIN 270-301 Page 4	BIOMARIN	270-301	Page 4
--------------------------------	----------	---------	--------

NAME OF COMPANY BioMarin Pharmaceutical Inc. [name]	SUMMARY TABLE Referring to Part of the Dossier:	FOR NATIONAL AUTHORITY USE ONLY:
	Volume:	
NAME OF FINISHED PRODUCT: BMN 270	Page:	
NAME OF ACTIVE INGREDIENT: AAV5-hFVIII-SQ	Reference:	

Figure 1. hFVIII-SQ Vector Genome Schematic

Legend –Note that schematic is not to scale; nt = nucleotides

BMN 270 will be delivered by a single intravenous dose and is designed to achieve stable, potentially life-long expression of active hFVIII in the plasma, synthesized from vector-transduced liver tissue.

BMN 270 is currently being evaluated in clinical study 270-201, an ongoing first-in-human, phase 1/2 dose escalation study in subjects with severe HA designed to assess the safety and efficacy of BMN 270 at various dose levels (6E12 vg/kg, 2E13 vg/kg, 4E13 vg/kg, 6E13 vg/kg). Specifically, 270-201 explores the relationship of vector dose to the augmentation of residual FVIII activity and whether these levels are sufficient to alter the clinical phenotype. Preliminary results from 270-201 have demonstrated that following gene transfer, FVIII activity above 5% (5 IU/dL) and, in many cases, within the normal range for FVIII, is achievable at doses of 4-6E13 vg/kg with an acceptable safety profile (Pasi, 2016, Haemophilia).

The current study is a Phase 3, single-arm, open-label study designed to assess whether, in an expanded sample, BMN 270 can safely alter the clinical phenotype of hemophilia A patients with residual FVIII activity ≤ 1 IU/dL, with an altered phenotype defined as achieving FVIII activity of $\geq 5\%$ (5 IU/dL).

OBJECTIVES:

The primary efficacy objectives of the study are to:

• Assess the efficacy of BMN 270 defined as median FVIII activity during Weeks 48-52 following intravenous infusion of BMN 270

The secondary efficacy objectives of the study are to:

 Assess the impact of BMN 270 on usage of exogenous FVIII replacement therapy from Week 5 to Week 52

|--|

NAME OF COMPANY BioMarin Pharmaceutical Inc. [name]	SUMMARY TABLE Referring to Part of the Dossier:	FOR NATIONAL AUTHORITY USE ONLY:
[name] NAME OF FINISHED PRODUCT: BMN 270	Volume: Page:	
NAME OF ACTIVE INGREDIENT: AAV5-hFVIII-SQ	Reference:	

• Assess the impact of BMN 270 on the number of bleeding episodes requiring exogenous FVIII replacement therapy from Week 5 to Week 52

The tertiary efficacy objectives of the study are to:

• Assess the impact of BMN 270 on patient-reported outcomes (PROs) at Week 52 of the study compared to baseline

The safety objectives of the study are to:

- Evaluate the safety of BMN 270 during the first 52 weeks following intravenous infusion
- Assess the long-term safety of BMN 270

STUDY DESIGN AND PLAN:

This is a Phase 3, single-arm, open-label study in hemophilia A patients with residual FVIII levels ≤ 1 IU/dL treated continuously with prophylactic exogenous FVIII for the year prior to enrollment. Subjects will be enrolled at approximately 30 sites worldwide. Subjects must have high-quality, well-documented historical data available concerning previous bleeding episodes and exogenous FVIII usage over the previous 12 months in order to be eligible to enroll in the study.

Approximately 40 subjects will receive a 6E13 vg/kg dose of BMN 270 as an intravenous infusion. The Data Monitoring Committee (DMC) will review available safety and efficacy (eg, FVIII activity) data during the study on an ongoing basis and may determine, based on emerging data and the risk/benefit profile, that further enrollment at 6E13 vg/kg should be discontinued in favor of a different dose of BMN 270. If the DMC recommends a dosing modification, then additional subjects may be enrolled, up to a total of approximately 40 subjects, at the new BMN 270 dose level (regardless of the number of subjects previously enrolled at 6E13 vg/kg).

An interim analysis will be performed after all subjects have been followed for 26 weeks post-BMN 270 infusion.

The final analysis for the study will be performed after all subjects have been followed for 52 weeks post-BMN 270 infusion. After the final analysis, safety and efficacy will then continue to be assessed long-term in all subjects for a total of approximately 5 years.

To avoid breakthrough bleeding, subjects will only discontinue exogenous prophylactic FVIII replacement therapy after FVIII activity has reached at least 5 IU/dL or 4 weeks following infusion of BMN 270, whichever is earlier. Four weeks represents the time by which endogenous production of FVIII following gene transfer is expected to be efficacious.

Throughout the study, subjects with FVIII activity below 5 IU/dL may be monitored more frequently at the discretion of the Medical Monitor and the Investigator.

BIOMARIN 270-301 Page 6

NAME OF COMPANY BioMarin Pharmaceutical Inc. [name]	SUMMARY TABLE Referring to Part of the Dossier:	FOR NATIONAL AUTHORITY USE ONLY:
[name] NAME OF FINISHED PRODUCT: BMN 270	Volume: Page:	
NAME OF ACTIVE INGREDIENT: AAV5-hFVIII-SQ	Reference:	

There will be an ongoing review of individual subject safety and efficacy data by the Medical Monitor and the DMC. FVIII activity by a validated assay will be used to evaluate efficacy over the course of the study. Therapeutic oral corticosteroids may be initiated when a subject's ALT values are elevated or based on review of FVIII activity and liver enzyme data, and subsequent dosage adjustments made, after consultation between the Investigator and the Medical Monitor. Any safety signal may trigger a review of the data and possible additional immunogenicity studies or other diagnostics deemed necessary that include an assessment of cellular immune responses using collected peripheral blood mononuclear cells (PBMCs).

NUMBER OF SUBJECTS PLANNED:

Approximately 40 subjects may enroll into the study.

DIAGNOSIS AND ALL CRITERIA FOR INCLUSION AND EXCLUSION:

Participants are eligible to be included in the study only if all of the following criteria apply:

- 1. Males \geq 18 years of age with hemophilia A and residual FVIII levels \leq 1 IU/dL as evidenced by medical history, at the time of signing the informed consent.
- 2. Must have been on prophylactic FVIII replacement therapy for at least 12 months prior to study entry. High-quality, well-documented historical data concerning bleeding episodes and FVIII usage over the previous 12 months must be available.
- 3. Treated/exposed to FVIII concentrates or cryoprecipitate for a minimum of 150 exposure days (EDs).
- 4. Willing and able to provide written, signed informed consent after the nature of the study has been explained and prior to any study-related procedures.
- 5. No history of FVIII inhibitor, and results from a Bethesda assay with Nijmegen modification of less than 0.6 Bethesda Units (BU) on 2 consecutive occasions (the most recent one of which should be tested at the central laboratory) at least one week apart within the past 12 months
- 6. Sexually active participants must agree to use an acceptable method of double barrier contraception for at least 6 months post-infusion, which may include hormonal contraception for a female partner. After 6 months, subjects may stop contraception use only if they have had 3 consecutive semen samples with no detectable viral vector DNA.
- 7. Willing to abstain from alcohol consumption for at least the first 52 weeks following BMN 270 infusion.

BIOMARIN 270-301 Page 7

NAME OF COMPANY	SUMMARY TABLE	FOR NATIONAL
BioMarin Pharmaceutical Inc.	Referring to Part of the	AUTHORITY USE
[name]	Dossier:	ONLY:
[name]		
	Volume:	
NAME OF FINISHED PRODUCT:		
BMN 270	Page:	
NAME OF ACTIVE INGREDIENT:	Reference:	
AAV5-hFVIII-SQ		

8. HIV positive patients may be enrolled, only if the patient has a CD4 count > 200/mm³ and an undetectable viral load.

Participants are excluded from the study if any of the following criteria apply:

- 1. Detectable pre-existing antibodies to the AAV5 capsid.
- 2. Any evidence of active infection or any immunosuppressive disorder, except for HIV infection as described in the inclusion criterion above.
- 3. Significant liver dysfunction with any of the following abnormal laboratory results:
 - ALT (alanine transaminase) or AST >2X ULN;
 - Total bilirubin >2X ULN;
 - Alkaline phosphatase >2X ULN; or
 - INR (international normalized ratio) ≥ 1.4 .

Subjects whose liver laboratory assessments fall outside of these ranges may undergo repeat testing and, if eligibility criteria are met on retest, may be enrolled after confirmation by the Medical Monitor. In addition, subjects with abnormal laboratory results related to confirmed benign liver conditions (eg, Gilbert's syndrome) are considered eligible for the study notwithstanding their abnormal laboratory results and may be enrolled after discussion with the Medical Monitor.

- 4. Prior liver biopsy showing significant fibrosis of 3 or 4 as rated on a scale of 0-4 on the Batts-Ludwig (Batts 1995) or METAVIR (Bedossa 1996) scoring systems, or an equivalent grade of fibrosis if an alternative scale is used.
- 5. Evidence of any bleeding disorder not related to hemophilia A.
- 6. Platelet count of $< 100 \times 10^9/L$.
- 7. Creatinine $\geq 1.5 \text{ mg/dL}$.
- 8. Liver cirrhosis of any etiology as assessed by liver ultrasound.
